- b) Subjects with any bacterial infection within the last 60 days prior to screening (enrollment), unless treated and resolved with antibiotics, or any chronic or history of recurrent bacterial infection (such as chronic pyelonephritis, osteomyelitis and bronchiectasis)
- c) Subjects who have a history of systemic fungal infections (such as histoplasmosis, blastomycosis, or coccidioidomycosis)
- d) Subjects with history of recurrent herpes zoster (more than 1 episode) or disseminated (more than 1 dermatome) herpes zoster or disseminated herpes simplex, or ophthalmic zoster will be excluded. Symptoms of herpes zoster or herpes simplex must have resolved more than 60 days prior to screening visit (enrollment)
- e) Subjects with evidence (as assessed by the investigator) of active or latent bacterial or viral infection at the time of potential enrollment, including subjects with history or evidence of Human Immunodeficiency Virus (HIV) infection or who have a positive HIV test at screening
- f) Any significant concurrent medical condition at the time of screening or baseline visit, including, but not limited to, the following:
 - i) Any major illness/condition or evidence of an unstable clinical condition (eg, renal, hepatic, hematologic, gastrointestinal, endocrine, pulmonary or active infection/infectious illness) that, in the Investigator's judgment will substantially increase the risk to the subject if he or she participates in the study
 - ii) Cancer or lymphoproliferative disease within the previous 5 years (other than resected cutaneous basal cell or squamous cell carcinoma that has been treated with no evidence of recurrence). Subjects with a history of lymphoma at any time are excluded
 - iii) Female subjects with a breast cancer screening suspicious for malignancy, and in whom the possibility of malignancy cannot be reasonably excluded following additional clinical, laboratory or other diagnostic evaluations
 - iv) Class III or IV congestive heart failure as defined by the New York Heart Association
 - v) Acute coronary syndrome (eg, myocardial infarction, unstable angina pectoris) and/or any history of significant cerebrovascular disease within 24 weeks before screening
 - vi) Liver cirrhosis or other underlying liver disease (eg, non-alcoholic steatohepatitis, primary sclerosing cholangitis, primary biliary cirrhosis/cholangitis)
 - vii) Any significant coagulation or platelet function disorders (eg, von Willebrand's disease)

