 - (1) WBC count $< 3000/\text{mm}^3$ ($3.0 \times 10^9/\text{L}$)

- (2) Hemoglobin < 9 g/dL
- (3) Absolute neutrophil count < 1000/mm³ (1.0 x 10⁹/L)
- (4) Platelets < 100,000/mm³ (100 x 10⁹/L)
- iii) Creatinine ≥ 2.0 mg/dL
- e) Subjects with a positive TB IGRA (such as Quantiferon® TB Gold, Refer to [Section 3.3.2 #2a](#))
- f) Any other significant laboratory abnormalities that, in the opinion of the Investigator, might place the subject at unacceptable risk for participation in this study (please discuss with BMS Medical Monitor if there are any questions in regards to inclusion/exclusion criteria)

4. Allergies and Adverse Drug Reaction

- a) History of any significant drug allergy (such as anaphylaxis or hepatotoxicity)

5. Prior and Concomitant Medications

- a) Oral corticosteroids > 10 mg/day within 14 days of dosing (Day 1), or corticosteroid therapy ≥ 1 mg/kg during the 4 weeks preceding enrollment
- b) Intravenous, intramuscular or intra-articular corticosteroids within 4 weeks of enrollment
- c) Treatment started or an unstable dose of non-steroidal anti-inflammatory drugs (NSAIDs), pilocarpine, cevimeline (Evoxac®), topical corticosteroid eye preparations, lifitegrast (Xiidra®), autologous serum eye drops, or cyclosporine eye drops (Restasis®) within 14 days of dosing (doses must be held for at least 12 hours prior to any study visit after Screening)
- d) Use of methotrexate, cyclophosphamide, cyclosporine, tacrolimus, azathioprine, mycophenolate mofetil (MMF) or leflunomide within 12 weeks of enrollment
- e) Treatment started or an unstable dose of hydroxychloroquine (Plaquenil®) within 8 weeks of enrollment. Doses higher than 400 mg/day are not permitted. Use of other antimalarials (eg, chloroquine, quinacrine) is not permitted
- f) Use of rituximab within 6 months prior to enrollment or lack of recovery of CD19+ B cells to > 10/μl at screening in any subject with prior rituximab use
- g) Previous treatment with other biologics either marketed or in development (eg, abatacept, tocilizumab, belimumab, TNF inhibitors) within 6 months prior to enrollment
- h) Subjects are not permitted to have new installation of lacrimal punctum plugs within 4 weeks of randomization (Day 1) or during the course of the study. Subjects with existing lacrimal punctum plugs are permitted to enroll, and have these plugs replaced as necessary during the study

6. Other Exclusion Criteria

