3.5 Discontinuation of Subjects Following Treatment with Study Drug

Subjects MUST discontinue investigational product (and non-investigational product at the discretion of the investigator) for any of the following reasons:

- Subject's request to stop study treatment or withdrawal of informed consent
- Any clinical adverse event (AE), laboratory abnormality or intercurrent illness which, in the opinion of the investigator, indicates that continued participation in the study is not in the best interest of the subject
- Termination of the study by Bristol-Myers Squibb (BMS)
- Loss of ability to freely provide consent through imprisonment or involuntarily incarceration for treatment of either a psychiatric or physical (eg, infectious disease) illness
- Unblinding a subject for any reason (emergency or non-emergency)
- Use of prohibited medication
- Development of new active manifestations of pSS requiring treatment with any non-protocol approved medications during the study
- Inability or subject's failure to comply with the protocol requirements
- Pregnancy
- Male subjects must discontinue treatment if their female partners become pregnant during the trial. After discontinuation, male subjects are required to continue using a highly effective method of contraception for a total of 35 days post-treatment completion
- Severe (eg, \geq Grade 3), drug-related AEs of infection, bleeding events/coagulopathy, or injection site reactions

- ANC < 500/mm³, confirmed by repeat
- Potential drug induced liver injury (see [Section 6.6](#) for definition)

In the case of pregnancy, the investigator must immediately notify the BMS Medical Monitor/designee of this event. In most cases, the study drug will be permanently discontinued in an appropriate manner (eg, dose tapering if necessary for subject safety). Please call the BMS Medical Monitor/designee within 24 hours of awareness of the pregnancy. If the investigator determines a possible favorable benefit/risk ratio that warrants continuation of study drug, a discussion between the investigator and the BMS Medical Monitor/designee must occur.

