Only data for the procedures and assessments specified in this protocol should be submitted to BMS on a case report form. Additional procedures and assessments may be performed as part of

your institutional or medical practice standard of care; however, data for these assessments should remain in the subject’s medical record and should not be provided to BMS, unless specifically requested from the sponsor.

Safety assessments will be based on medical review of adverse event reports and the results of vital sign measurements, ECGs, physical examinations, and clinical laboratory tests. The severity of observed adverse events will be graded by National Cancer Institute’s Common Terminology Criteria for Adverse Events (NCI CTCAE) version 4.03. The incidence of observed adverse events will be tabulated and reviewed for potential significance and clinical importance.

Ongoing assessment of safety will be performed by an independent Data Monitoring Committee (DMC). The DMC may make recommendations to the Sponsor regarding conduct of the study based on safety observations.

5.3.1 **Imaging Assessment for the Study**

Not Applicable.

5.3.2 **Laboratory Testing**

A central/local laboratory will perform the analyses and will provide reference ranges for these tests.

All scheduled, routine safety laboratory testing should be performed after a minimum 10 hour fast. Detailed instructions on the collection, processing, and shipping of all blood and urine samples will be provided to the investigator in a separate manual at or before the time of study initiation.

The following clinical laboratory tests will be performed:

Hematology	
Hemoglobin	
Hematocrit	
Total leukocyte count, including differential	
Platelet count TBNK for CD19+ B cell count (screening only, for subjects with prior rituximab use)	
PT/PTT (screening only)	
Serum Chemistry	
Aspartate aminotransferase (AST) Alanine aminotransferase (ALT) Total bilirubin Direct bilirubin Alkaline phosphatase Lactate dehydrogenase (LDH) Creatinine Blood Urea Nitrogen (BUN) Uric acid Fasting glucose Lipase (screening only)	Total Protein Albumin Sodium Potassium Chloride Calcium Phosphorus Magnesium Creatine kinase Amylase (screening only)

Fasting lipid panel: total cholesterol, HDL-cholesterol, LDL-cholesterol, triglycerides (Day 1, Week 8, Week 12 and Follow-Up Week 18 only) ESR (local test) hsCRP
Urinalysis

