7.4.8 Anticoagulants

A summary of use of anticoagulants will be provided. This summary will include only prior medications (see [sections 7.3.4](#) for definition). The number and percent of subjects receiving anticoagulants as prior medication will be summarized by treatment group for MITT analysis population.

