7.6.1.1 Adverse Events

All serious and non-serious adverse events with onset during the double-blind treatment period will be summarized by SOC, PT, and treatment group and overall. These summaries will be produced for:

- all adverse events
- adverse events related to the administration of the study drug, as determined by the investigator
- adverse events leading to discontinuation of study medication, as indicated in the eCRF. This analysis will include events independently of the time distance the last dose date.
- most common adverse events (reported in 10% of subjects or more in any treatment group)
- all serious adverse events, as captured on special CRF pages
- all serious adverse events related to the administration of the study drug, as captured on special CRF pages
- adverse events by intensity, as determined by the investigator

The following adverse events of special interest will be summarized by PT and treatment groups during the double-blind period. A subject listing will also be provided.

- Infections: All reported infections and infestations within the SOC: *Infections and infestations*. The severity of serious infections will be summarized. In addition, a listing of opportunistic infections will be provided.

- Injection Reactions (Local and Systemic): All reported events defined in pre-specified MedDRA code of local and systemic injection reactions.

Additionally, a subject listing will be provided for the following adverse events of special interest that occurred during the double-blind period:

- Malignancy: All reported events defined in MedDRA Maintenance and Support Services Organization (MSSO) Structured MedDRA Query (SMQ) list.
- Autoimmunity: All reported events defined in pre-specified MedDRA code of autoimmune disorders.
- Transaminases Increased: All reported events defined in MedDRA Maintenance and Support Services Organization (MSSO) Structured MedDRA Query (SMQ) list. of “Drug related hepatic disorders - comprehensive search (SMQ)”

In addition, the number and proportion of subjects who experienced an AE once or multiple times (0 Events, 1 Events, 2-3 Events, ≥ 4 Events) will be summarized by PT and treatment groups for most common AE (at least 5% subject in any treatment group) and events of special interest of infections. This analyses will be performed following the counting rules for unique adverse events as described [section 8.18.2](#).

The following subject listings will be produced for:

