8.18 Counting rules for adverse events

8.18.1 At Subject Level

Where a subject has multiple adverse events within the same system organ class in a single analysis period, the subject will only be counted once at the system organ class level in adverse event frequency tables.

When a subject has the same adverse event, based on preferred terminology, reported multiple times in a single analysis period, the following criteria, in order of precedence, will be used to select the event to be included in summary tables:

- Relationship to study medication
- Intensity of event
- Onset date and time

When assessing relationship to study medication, relationship as reported by the investigator, events will be reported as related or not to study medication. Related events will take precedence over unrelated events in determining the event to include in summary tables.

More intense events will take precedence over less intense events in determining the event to include in summary tables.

Earlier onset date-time events will take precedence over late onset date-time events in determining the onset to include in summary tables.

When reporting adverse events by intensity, in addition to providing a summary table based on the event selection criteria detailed above, summary tables will also be provided based on the most intense event during the analysis period - independent of relationship to study medication. For these tables, the following criteria, in order of precedence, will be used to select the event to be included in summary tables:

- Intensity of event
- Onset date and time

Subjects will only be counted once in the ‘Total’ at their maximum intensity, regardless of SOC or PT.

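### Bleeding/coagulopathy is a mandatory-stop harm in Protocol 3.5, but SAP 7.6.1.1 defines no bleeding group and no per-arm count of subjects with any bleeding

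*SAP*

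**What the plan says.** Protocol 3.5 lists the reasons for which study drug must be stopped. One bullet names three harms together: severe (Grade 3 or above is the example given) "drug-related AEs of infection, bleeding events/coagulopathy, or injection site reactions".

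Bleeding risk is also touched on elsewhere. Protocol 3.3.2 excludes subjects with "Any significant coagulation or platelet function disorders" and, among the hematology limits, those with "Platelets < 100,000/mm³". Protocol 5.3.2 schedules prothrombin and partial thromboplastin times at screening only. SAP 7.4.8 says "A summary of use of anticoagulants will be provided", restricted to prior medication.

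SAP 7.6.1.1 plans tables by SOC, preferred term and arm for all, related, discontinuation-causing, common, serious and intensity-graded events. For events of special interest it says "The following adverse events of special interest will be summarized by PT and treatment groups during the double-blind period", and the groups that follow are infections and injection reactions (local and systemic). Malignancy, autoimmunity and increased transaminases get a listing only. The named subject listings cover infections, malignancies, autoimmune disorders and local and systemic injection reactions. Bleeding is in none of these.

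On counting, SAP 8.18.1 says that when a subject has several events in one SOC, "the subject will only be counted once at the system organ class level in adverse event frequency tables". Repeats of one preferred term are reduced to a single selected event. Protocol 8.4.3 commits to listing and summarizing events of special interest that were established in advance.

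**The concern.** The protocol treats bleeding/coagulopathy as serious enough to end treatment, on the same line as two harms for which the SAP defines an event group with a summary and a listing. Bleeding has no such group. The other specific safety stops in Protocol 3.5 each have some dedicated output: neutrophils in SAP Appendix 3, liver injury through the transaminase listing in 7.6.1.1, pregnancy through the listing in 7.6.2.3.

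Safety and tolerability are a secondary objective. A reader who asks how many subjects per arm had any bleeding event would have to rebuild the answer from the adverse event listing, with terms chosen after the data are known unless a standard query is used. No efficacy estimate, decision rule or stopping criterion is affected.

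**Working it through.** The plan gives no bleeding rate and no figure on this point, so the check is mainly a reading of the planned outputs. The arm sizes come from Protocol 8.1: 25 per arm as planned, 40 per arm at the maximum of 120. The power figures there reproduce with the noncentral t (0.901 against about 90%; 0.788 against 79%) and do not bear on the bleeding question.

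**Step 1: which outputs could count subjects with any bleeding?**
- General SOC and preferred-term tables: bleeding shows as individual terms under their SOCs. A subject is counted once within a SOC and once per term. No rule counts a subject once across SOCs for a chosen topic.
- Special-interest summaries and listings (SAP 7.6.1.1): no bleeding group.
- Laboratory output: SAP Appendix 3 has prothrombin, aPTT and INR ratio criteria, but these clotting times are scheduled at screening only. Platelet counts are followed, but a platelet count is not a bleeding event.

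Visible planned rows giving subjects with any bleeding per arm: 0.

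Infections differ because the SAP defines them as one whole SOC, so the ordinary table already gives a once-per-subject count. Injection reactions get a table by preferred term, and no any-event row is stated for them either. Adding bleeding on the same terms would therefore supply a fixed definition but not the missing count.

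**Step 2: how far can preferred-term rows mislead? (illustration)**
Assume bleeding terms are spread over several preferred terms and SOCs. Then k rows of one subject each represent between 1 and k distinct subjects. Exact (Clopper-Pearson) 95% limits for x of n are the 0.025 quantile of Beta(x, n−x+1) and the 0.975 quantile of Beta(x+1, n−x).

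| Subjects | n = 25 | n = 40 |
|---|---|---|
| 1 | 4.0% (0.1 to 20.4) | 2.5% (0.1 to 13.2) |
| 2 | 8.0% (1.0 to 26.0) | |
| 4 | 16.0% (4.5 to 36.1) | |
| 6 | 24.0% (9.4 to 45.1) | 15.0% (5.7 to 29.8) |

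Six single-subject rows are thus compatible with 4% to 24% of an arm of 25, or 2.5% to 15% of an arm of 40.

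**Step 3: the common-event tables**
If the 10% threshold is applied by preferred term, it needs 3 subjects of 25 (0.10 × 25 = 2.5, rounded up) or 4 of 40. The 5% once-or-multiple table needs 2 of 25 (0.05 × 25 = 1.25, rounded up) or 2 of 40. Six different subjects with one bleeding term each sit at 4% per term (n = 25) or 2.5% (n = 40). They give no preferred-term row in either table, although they are 24% or 15% of the arm. The all-event table still shows every one of them.

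**Step 4: the same point as a probability (illustration)**
Assume 25 per arm and a true any-bleeding risk p, with one term per affected subject, split evenly over five terms. Each term then has risk p/5, and P(X ≥ 3) is the binomial tail with n = 25.

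| p | A given term reaches 3 of 25 | A grouped row reaches 3 of 25 |
|---|---|---|
| 10% | 1.3% | 46.3% |
| 20% | 7.6% | 90.2% |
| 30% | 18.7% | 99.1% |

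The first column is for one given term. At p = 20%, the chance that at least one of the five reaches the line is at most 5 × 7.6% = 38%.

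**The case against.** The case against is substantial, and most of it stands.

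- *Nothing is breached.* Protocol 8.4.3 covers only events of special interest established in advance. No visible text names bleeding as one, and nothing says the stop list and the special-interest list must match. They serve different purposes: malignancy and autoimmunity are special-interest events without being named in Protocol 3.5. This stands.
- *The harm in the stop bullet is already reported.* A severe drug-related bleed that ends treatment enters the related, discontinuation and intensity tables and the discontinuation and all-event listings; a serious one also gets a narrative. With 25 to 40 subjects per arm, such cases can be counted by hand. This stands. A reader might infer from the missing group that bleeding goes unreported, or that the SAP departs from the protocol; the documents support neither.
- *The contrast with the other two harms is uneven.* It is weaker for injection reactions, which have a defined group but no stated any-event row. This stands, and it is why the row must be asked for explicitly.
- *The supporting signals are modest.* The platelet limit and clotting tests sit in routine screening panels, and the anticoagulant summary covers prior use only. They show awareness of bleeding, not a planned endpoint.
- *The absence cannot be proved.* SAP 7.6 defers to the sponsor's standard safety conventions, which are not reproduced. The monitoring committee's charter is not visible either. The claim is therefore limited to the visible plan.

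What survives is narrow: reporting by term does not give subjects with any bleeding, and no definition is fixed in advance. A standard query could be run later without choosing terms from the data, but fixing it now removes the question.

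**Conclusion.** The point holds as a cheap improvement to safety reporting. SAP 7.6.1.1 defines special-interest groups for infection and injection reactions but not for bleeding/coagulopathy, which Protocol 3.5 names in the same mandatory-stop bullet. The visible plan therefore has no pre-defined bleeding group and no per-arm count of subjects with at least one such event.

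The missing count rests on the assumption that bleeding terms fall in more than one SOC; the documents do not show how the terms are placed. The percentages above are illustrations of what term rows can hide, not estimates of bleeding in this trial. Confidence is medium, because the sponsor's unseen conventions may already supply the grouping.

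**What to change.** Add to the summarized and listed events in SAP 7.6.1.1: *Bleeding/coagulopathy: all reported events in the MedDRA haemorrhage SMQ, or a preferred-term list fixed before unblinding.* The SAP already uses SMQs for malignancy and transaminases, so the device is familiar.

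State three outputs:
- one row per arm for subjects with at least one such event, each counted once whatever the SOC (a table by preferred term does not produce this by itself);
- the same count by severity;
- a subject listing of all bleeding/coagulopathy events.

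If the standard safety conventions already contain this, cite them in 7.6.1.1 instead.

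The cost is one table, one listing and a blinded medical review of the term list. The data are already collected; no visit, procedure, staff or subject is added, and no efficacy analysis changes.

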NOTE: combination products including acetaminophen and narcotic analgesics (eg, acetaminophen with codeine phosphate, acetaminophen with propoxyphene napsylate, acetaminophen with oxycodone HCl, acetaminophen with hydrocodone bitartrate, etc.) are allowed provided the acetaminophen component dosage is accounted for in the maximum of 2 g/day
 - Narcotic analgesics must not exceed 30 mg/day of morphine or its equivalent
 - Tramadol doses must be stable
 - Acetylsalicylic acid is allowed in low doses (eg, ≤ 100 mg/day) for cardiovascular prophylaxis

Immunosuppressives

The following medications are prohibited during the screening, dosing and follow-up periods:

- methotrexate
- cyclophosphamide
- leflunomide
- azathioprine
- cyclosporine
- tacrolimus
- MMF
- rituximab
- belimumab
- tocilizumab

- All investigational and approved biologic therapies (including but not limited to abatacept, etanercept, anakinra, infliximab, etc.)
- Use of any investigational drug other than study medication

Hormonal Contraceptives:

The use of hormonal contraceptives (oral, via implant/depot or via eluting IUD) are prohibited as a method of highly effective contraception due to safety concerns from transient liver function test elevations observed in the drug-drug interactions study (IM006032) with BMS-986142 and a combination oral contraceptive (ethinyl estradiol and the norethindrone acetate). In the study, a total of 10 of 16 subjects that were dosed with the oral contraceptive and BMS-986142 in combination had mild to moderate elevations of transaminases without an associated increase of total bilirubin. The majority of ALT elevations were < 3xULN. The maximum increase occurred in one subject with an ALT 5.8x ULN without accompanying total bilirubin elevation. Most subjects had no symptoms, however, 3 subjects had nausea, 2 subjects had vomiting and 1 had chills. All of the elevated transaminase levels returned to baseline. An evaluation of the cause of the transaminase elevation is ongoing, but no marked changes in the exposures of BMS-986142 or the components of the oral contraceptive were observed in a preliminary assessment of the data (i.e. no pharmacokinetic drug-drug interaction occurred during co-administration).

In addition, the use of oral or implantable estrogen-based hormone replacement therapy is also prohibited until additional drug interaction data becomes available. See Section 3.4.1.3.

[REDACTED]

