8.4.3 Safety Analyses

All recorded adverse events will be listed and tabulated by system organ class, preferred term, and treatment. Vital signs and clinical laboratory test results will be listed and summarized by treatment. Any significant physical examination findings, and clinical laboratory results will be listed. ECG readings will be evaluated by the investigator and abnormalities, if present, will be listed. Any pre-established Events of Special Interest will be listed and summarized.

[REDACTED]

[REDACTED]

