7.6 Safety

The safety analysis endpoints described in this section are considered as secondary endpoints. For their analysis, there will be no statistical testing of group.

Analysis of all safety data will follow the BMS standard safety data conventions^{34 35} and supplements to the standard conventions as defined in this document.

All summaries of safety parameters during the double-blind period will be provided by treatment groups. All safety assessments will be included in the summary tables if the onset date is on or after the first dose date and the event occurs within the double-blind period or within 42 days post last dose date.

Presentations for the double-blind period will be provided by “as treated” treatment group for the as-treated analysis population, unless otherwise specified.

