7.6.1 Adverse Events

All AEs are coded and grouped into Preferred Terms (PT) by System Organ Class (SOC), using the latest approved version of the Medical Dictionary for Regulatory Activities (MedDRA) at the time of database lock. Listings and summaries will be based on the resulting SOCs and PTs.

AEs will be included in the frequency tabulations if they occur while a subject is on study medication up to and including 42 days after the last dose of study medication of either active medications or matching placebos. These AE summaries will be based on proportions, which represent the number of subjects experiencing the AEs divided by the number of subjects received with at least 1 dose of study medication.

In summaries by SOC and PT, AEs will be sorted by decreasing frequency within each SOC and PT according to the Lulizumab group. In summaries by PT, AEs will be sorted by decreasing frequency within PT according to the Lulizumab group. Counting rules for adverse events are described in [section 8.18](#).

All adverse events listings will indicate the unique subject identifier, age, gender, current treatment, the date of onset, the date of resolution, day of onset relative to the start of treatment, action taken, investigator's assessment of severity and relationship to study drug.

Laboratory AEs are laboratory changes identified by the investigator as AEs and thus reported on the AE pages of the eCRF.

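### Three of the SAP's five groups of adverse events of special interest, including the hepatic one, are listed but not summarized by arm, although the protocol commits to both

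*SAP*

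**What the plan says.** Protocol 8.4.3 sets one rule, repeated in the synopsis: "Any pre-established Events of Special Interest will be listed and summarized". The protocol text available does not name the groups.

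SAP 7.6.1.1 names five and treats them in two ways.

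- Infections and injection reactions: "The following adverse events of special interest will be summarized by PT and treatment groups during the double-blind period". A subject listing is also promised.
- Malignancy, autoimmunity and Transaminases Increased: "Additionally, a subject listing will be provided for the following adverse events of special interest that occurred during the double-blind period". No summary is mentioned. The last of these is defined by the comprehensive SMQ search for drug-related hepatic disorders.

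The catalogue of listings that closes the section repeats infections, malignancies, autoimmune disorders and both kinds of injection reaction. It leaves out the hepatic group.

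**The concern.** The SAP calls all five groups events of special interest but gives three of them less than the protocol promises, and no visible text explains the difference. Safety and tolerability is a secondary objective.

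The hepatic group matters most. Protocol 3.4.1.2 reports from a drug interaction study that "a total of 10 of 16 subjects that were dosed with the oral contraceptive and BMS-986142 in combination had mild to moderate elevations of transaminases", and says that evaluation of the cause is ongoing. That makes liver events a natural subject for a grouped by-arm count. Without one, events coded to several terms appear as separate sparse rows, and a reader has to rebuild the group from a listing.

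**Working it through.** This is mainly a comparison of texts. No sample size, power or alpha figure enters the claim.

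**Step 1. Count the groups.** Five are named in SAP 7.6.1.1. Summarized by arm and listed: infections and injection reactions, 2 of 5. Listed only: malignancy, autoimmunity and Transaminases Increased, 3 of 5. Protocol 8.4.3 makes no such distinction.

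**Step 2. See what other planned output gives by arm for the liver.**

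| Output | Source | Grouped hepatic count? |
|---|---|---|
| All, related, serious and discontinuation AEs, and AEs by intensity, by SOC and PT | SAP 7.6.1.1 | No: rows are single PTs or whole SOCs |
| Subjects with marked abnormalities, per laboratory test | SAP 7.6.2.1, Appendix 3 | No: per test, and only beyond set limits |
| AST, ALT and bilirubin values and changes, by treatment and visit | SAP 7.6.2.2 | No: descriptive statistics, not subjects affected |

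**Step 3. Ask whether the rows can be combined.** SAP 8.18.1 counts a subject once per SOC, so terms within one SOC do roll up. Infections are defined as a whole SOC and therefore already have a grouped count. The other groups are defined by SMQ lists or pre-specified MedDRA codes, which need not match an SOC. Adding PT rows counts a subject with two terms twice.

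**Step 4. Size the ambiguity.** For any group, the number of subjects with at least one event lies between the largest PT row and the sum of the PT rows (at most the arm size). Take a hypothetical arm of 25 (the planned size, Protocol 8.1) with four hepatic PT rows of one subject each:

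- Each row: 1/25 = 4%.
- Lower bound, one subject with all four terms: 1/25 = 4% (exact 95% CI 0.1% to 20.4%).
- Upper bound, four different subjects: 4/25 = 16% (exact 95% CI 4.5% to 36.1%).

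At the maximum of 40 per arm, the same rows are 1/40 = 2.5% each and the upper bound is 4/40 = 10%. The PT table looks the same in both cases; only a grouped row separates them.

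**Step 5. Check the limits of the laboratory table.** With a normal baseline, Appendix 3 flags ALT and AST above 3 x ULN. Further criteria are above 4 x baseline when baseline exceeds ULN, and above 5 x ULN. Protocol 3.4.1.2 says that most ALT elevations in the interaction study were below 3 x ULN. Similar elevations here would mostly show in the by-visit summaries and in the listing of out-of-range results, or in AE tables if reported as AEs.

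**The case against.** A reader might infer that the SAP provides no by-arm liver rate at all. The documents contradict that. SAP 7.6.1.1 states: "All serious and non-serious adverse events with onset during the double-blind treatment period will be summarized by SOC, PT, and treatment group and overall". SAP 7.6.1 makes these subject proportions, "the number of subjects experiencing the AEs divided by the number of subjects received with at least 1 dose of study medication", and the all-AE table has no frequency threshold, so a term that misses the 10% table is still shown. Marked ALT, AST and bilirubin abnormalities are tabulated as subject frequencies, and SAP 7.6 says: "All summaries of safety parameters during the double-blind period will be provided by treatment groups".

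A reader might also take 10 of 16 (62.5%) as the rate to expect. It is not. It arose when BMS-986142 was given with an oral contraceptive, and Protocol 3.4.1.2 and Appendix 1 prohibit hormonal contraception for subjects who could become pregnant.

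Nor would the missing table close the gap below 3 x ULN. It would count reported AEs, and under SAP 7.6.1 a laboratory change becomes an AE only when the investigator identifies it as one.

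Other points have weight. The protocol promises a summary, not specifically a pooled any-event row; even the two summarized groups are specified by PT. The qualifier about events being pre-established leaves some room, and the sponsor's safety conventions cited in SAP 7.6 are not available. AE listings show treatment, so counts could be made by hand. Potential drug-induced liver injury is reported as an SAE (Protocol 6.6), with by-arm SAE tables and narratives, and the DMC reviews events of special interest.

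These arguments reduce the consequence but do not remove the mismatch. The SAP itself labels all five groups as events of special interest, and a hand count from a listing is not a planned summary.

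**Conclusion.** The point holds in a limited form. Three of five groups lack the by-arm summary that Protocol 8.4.3 commits to, and no planned table gives the number of subjects per arm with any event in those groups. The omission matters most for the hepatic SMQ.

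The consequence is modest. Safety is analysed descriptively without testing, and neither the primary analysis nor alpha is affected. In the hypothetical arm of 25, the planned rows leave a grouped hepatic incidence undetermined between 4% and 16%. The added row would itself be imprecise: 0/25 has an exact upper 95% limit of 13.7% (8.8% for 0/40).

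The conclusion assumes that the SMQ spans several PTs and may cross SOCs, since the SAP does not list its terms. It also assumes that the conventions cited in SAP 7.6 do not already require the table.

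**What to change.** In SAP 7.6.1.1, add malignancy, autoimmunity and Transaminases Increased to the by-arm summary of events of special interest. For each, give the number and percent of subjects with any event in the group, then by PT, using the As-Treated population as for the other safety tables. State the any-event row explicitly, because the existing wording provides for PT rows only. Keep the listings, and add the hepatic group to the closing catalogue of listings.

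The cost is three small tables from groups the SAP already defines, so minor programming time. Trial conduct does not change. The text should say that the hepatic table covers reported AEs only, with laboratory elevations described through SAP 7.6.2.
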